Best supportive care is allowed as a base therapy except the use of convalescent plasma, or anti-SARS-CoV-2 spike (S) protein targeted therapy. Refer to local clinical routine for the treatment of patients with severe COVID-19.

Criteria for Evaluation:

Efficacy: 8-Point ordinal scale.

Safety: Division of AIDS (DAIDS) Table for Grading the Severity of Adult and Pediatric Adverse Events (Version 2.1, July 2017).

Statistical Methods:

- All enrolled subjects set: All patients who sign the informed consent form (ICF) will be registered in the electronic data collection (EDC) system. Cases that are included in the study but not administered study drug will be analyzed using this analysis set.
- ITT set: All patients who are randomly assigned to and receive a dose of study drug. This is the primary analysis set for the efficacy analyses, and patients will be analyzed according to the treatment to which they are randomly assigned.
- Full analysis set (FAS): All patients who are randomly assigned, receive a dose of study drug and have at least one primary endpoint measurement. This analysis set will support the robustness of the primary efficacy results and patients will be analyzed according to the treatment to which they are randomly assigned.

- Safety set (SS): All patients who are randomly assigned and receive a dose of study drug. All safety analyses will be based on the safety set, with patients analyzed according to the treatment they received.
- Pharmacokinetics set (PKS): Subjects that receive single-dose investigational drug and have at least one blood-drug concentration data point which can be analyzed. PKS consists of PK Concentration set (PKCS) and PK Parameter set (PKPS).
- Per-protocol set (PPS): All patients in the ITT set without any major protocol deviations which may affect efficacy evaluation. The Per-protocol combined set will be used for sensitivity analysis of the primary endpoint.

Safety Analysis

The safety summaries will include treatment group and placebo group, comprising all patients in the safety set.

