1.5. Secondary Endpoints

- Clinical efficacy of SCTA01:
 - Proportion of patients with initial clinical improvement at Day 29 (Phase II, III);
 - Proportion of patients with sustained clinical improvement at Day 29 (Phase II, III);
 - Time to initial clinical improvement up to Day 29 (Phase II, III);
 - Time to discharge from hospital, followed by being alive and home for 14 consecutive days prior to Day 90 (Phase II, III);
 - Proportion of patients discharged from hospital, followed by being alive and home for 14 consecutive days prior to Day 90 (Phase II, III);
 - All-cause mortality up to Day 29, record date and cause of death (if applicable) (Phase II, III);

- Percentage of subjects in each category on the 8-point ordinal scale (time frame: Days 3, 5, 8, 11, 15, 22, and 29) (Phase II, III);
 - Proportion of patients alive and free of respiratory failure up to Day 29 (Phase II, III);
 - Proportion of patients who are discharged from acute care up to Day 29 (Phase II, III);
 - Days of supplemental oxygen (if applicable) up to Day 29 (Phase II, III);
 - Days of non-invasive ventilation/high flow oxygen (if applicable) up to Day 29 (Phase II, III);
 - Days of invasive mechanical ventilation/extracorporeal membrane oxygenation (ECMO) (if applicable) up to Day 29 (Phase II, III);
 - Time to hospital discharge up to Day 29 (Phase II, III);
 - Number and proportion of non-responders having mutations in the gene encoding the SARS-CoV-2 S protein through Day 29. A non-responder is defined as a patient who does not achieve a reduction in viral shedding or persistence viral presence or have a rebound in viral shedding following suppression (Phase II, III).
- Safety of SCTA01:
 - Cumulative incidence of serious adverse events (SAEs) (Phase II, III);
 - Cumulative incidence of Grade 1, 2, 3 and 4 clinical and/or laboratory adverse events (AEs) (Phase II, III);
 - Discontinuation or temporary suspension of infusions (for any reason) (Phase II, III);
 - Chemistries, hematology, urinalysis, coagulation function, IL-6, ferritin, procalcitonin, thrombin time, D-dimer (Phase II, III);
 - Number and proportion of patients who are suspected to experience antibody-dependent enhancement (ADE) (Phase II, III).
- Virologic efficacy of SCTA01:
 - Change from baseline in viral shedding as measured by quantitative reverse transcription polymerase chain reaction (RT-qPCR) in NP or OP swab samples (Phase II, III);

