3. INVESTIGATIONAL PLAN

3.1. Overall Study Design

The study is a multicenter, adaptive, randomized, double-blinded and placebo-controlled Phase II/III trial, and will be conducted at selected investigational sites globally.

Phase II part will evaluate the efficacy, safety, and PK of SCTA01 15 mg/kg, 50 mg/kg in patients with severe COVID-19. The primary endpoint will evaluate TTCI in study group 1 [SCTA01 15 mg/kg + best supportive care (BSC)], study group 2 (SCTA01 50 mg/kg + BSC) and control group (placebo + BSC) up to Day 29. The secondary endpoint will evaluate the virologic efficacy in study group 1 (SCTA01 15 mg/kg +BSC), study group 2 (SCTA01 50 mg/kg + BSC) and the control group (placebo + BSC) from baseline to Day 8, and then determine the recommended dose for Phase III part.

In the Phase II part of the study, 285 subjects will be randomized by 1:1:1 ratio to 15 mg/kg group, 50 mg/kg group and placebo group, with 95 subjects in each group.

At the end of Phase II part, enrollment will be paused and an interim analysis for dose selection will be performed after the 285th subject has been observed for TTCI. An IDMC will assess the benefit and risk to decide the dose for Phase III part of the part.

Enrollment will be resumed and the study continue into Phase III part after the IDMC has completed the evaluation and recommended the dose for Phase III part.

The Phase III part will evaluate the efficacy, safety, and immunogenicity of SCTA01 at the dosage recommended by the IDMC (X mg/kg or X mg) in severe patients with COVID-19. The primary endpoint will evaluate TTCI (8-point ordinal scale) in study group (SCTA01 X mg/kg or X mg + BSC) and control group (placebo + BSC) up to Day 29.

Approximately 510 subjects in Phase III part will be randomized by 1:1 ratio to SCTA01 (X mg/kg or X mg) and placebo, with 255 subjects in each group. The IDMC will be used to monitor safety and efficacy information.

Total number of subjects in the study is about 795.

Interim analysis (IA): There will be three un-blinded interim analyses when 143rd patient in Phase II has completed Day 8 visit, at the end of Phase II and when the 160th patient in Phase III has completed Day 29 or Early Withdraw visit.

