5.6. Randomization and Blinding

Each subject will be assigned a unique identification number. The subject identification (SID) number will be used to identify the subject throughout the study and will be entered on all study documentation. The SID will be an 8-digit number with the first 4 digits corresponding to the site number and the last 4 digits sequentially assigned by the site at screening. If a subject discontinues from the study at any time, his/her study number cannot be reassigned to another subject.

Phase II part of the study: Patients will be randomly assigned to receive SCTA01 (15 mg/kg), SCTA01 (50 mg/kg) or placebo a 1:1:1 ratio. The randomization schedule will be stratified by country.

Phase III part of the study: Patients will be randomly assigned to receive SCTA01 (X mg/kg or X mg) or placebo in a 1:1 ratio. The randomization schedule will be stratified by country.

An interactive web response system (IWRS) will be used to administer the randomization schedule. An independent CRO statistician will generate a permuted block randomization schedule for IWRS, which will link the sequential patient randomization numbers to the treatment codes.

Each patient will be assigned a randomization number which is different from the patient identification number. Once a randomization number has been allocated to a patient, it cannot be assigned to another patient.

To ensure the treatment assignment is unbiased and concealed from all individuals involved in the study, all enrolled patients are randomized to SCTA01 or placebo group using the following procedures: 1) randomization data are kept strictly confidential until the time of final analyses, and will not be accessible to anyone involved in the conduct of the study with the exception of the IDMC team and unblinded statistician; 2) the identity of the treatments will be concealed by the use of study drugs (SCTA01 and Matching Placebo) that are all identical in packaging, labeling, schedule of administration and appearance.

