9.6. Safety Analysis

The general safety summaries will include treatment group and placebo group, comprising all patients in the safety set.

Adverse events will be tabulated by treatment group. The number and percentage of patients with at least one AE will be presented along with a breakdown by system organ class (SOC) and Preferred Term (PT), with each patient being counted once at each summarization level. This summary will be repeated for treatment-related AEs, AEs that lead to study drug discontinuation, by relationship to study drug, by intensity and for SAEs.

Laboratory test results, vital signs data, and ECG data will be presented in tables summarizing absolute values and change from baseline by treatment group, with shift tables included as appropriate.

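### Safety summaries are not separated by phase although SCTA01:placebo allocation is 2:1 in Phase II and 1:1 in Phase III, so part of any between-phase change in event rates can look like a drug difference

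*Combined protocol and SAP*

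**What the plan says.** Section 9.6 of the protocol defines the safety displays in one sentence: "The general safety summaries will include treatment group and placebo group, comprising all patients in the safety set". The Safety Analysis part of the synopsis repeats it: "The safety summaries will include treatment group and placebo group, comprising all patients in the safety set". Section 9.6 continues: "Adverse events will be tabulated by treatment group", with numbers and percentages of patients. The synopsis definition of the safety set covers every randomized and dosed patient without reference to phase, and adds: "All safety analyses will be based on the safety set, with patients analyzed according to the treatment they received".

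The allocation differs between the two parts. Section 5.6 says for Phase II: "Patients will be randomly assigned to receive SCTA01 (15 mg/kg), SCTA01 (50 mg/kg) or placebo a 1:1:1 ratio". Section 3.1 gives the sizes. For Phase II: "285 subjects will be randomized by 1:1:1 ratio to 15 mg/kg group, 50 mg/kg group and placebo group, with 95 subjects in each group". For Phase III, where the last figure is per arm: "Approximately 510 subjects in Phase III part will be randomized by 1:1 ratio to SCTA01 (X mg/kg or X mg) and placebo, with 255 subjects". Enrolment stops between the two parts while the dose is chosen.

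Section 1.5 assigns the safety endpoints, including SAEs, graded AEs and suspected antibody-dependent enhancement, to both phases. No section presents safety by phase, weights or stratifies it by phase, or states whether 15 mg/kg and 50 mg/kg are shown together or apart.

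**The concern.** When the active to placebo ratio changes between two recruitment periods, a crude table over both periods gives the two columns different mixes of early and late patients. If the underlying event rate also changes, the columns differ even when the drug does nothing.

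The protocol itself gives reasons why rates could change:
- Recruitment is paused and then resumed (section 3.1).
- An early safety signal may influence who is enrolled (section 3.1).
- Premedication may be introduced for later participants if infusion reactions warrant it (section 3.4).
- Best supportive care follows local policy (section 3.6.2).

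At stake is how SAE, AE and suspected-enhancement proportions are read. A spurious excess on SCTA01 could look like harm, and a change in the other direction could hide harm. Merging the doses would also dilute any dose-related toxicity in the final tables.

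The primary efficacy analysis does not have this problem. Section 9.3 leaves the dropped dose out of the comparison, so allocation is 1:1 in both phases, and section 9.7.2 combines the phases through stage-wise p-values. Section 9.6 states no counterpart for safety.

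**Working it through.** **Inputs.** Phase II: 95 per group, three groups. Phase III: 255 per group, two groups (section 3.1). I assume that all randomized patients are dosed as assigned, that recruitment is completed, and that the Phase III dose is tabulated with the Phase II dose it continues.

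**Reproducing the plan's counts.** 3 × 95 = 285; 2 × 255 = 510; 285 + 510 = 795; 95 + 255 = 350 per arm in the primary comparison (section 9.3). All agree with the protocol. It gives no figure for the safety comparison.

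**Reading 1: both doses in one SCTA01 column.**
- SCTA01: 190 + 255 = 445, of whom 190/445 = 42.7% are from Phase II.
- Placebo: 95 + 255 = 350, of whom 95/350 = 27.1% are from Phase II.

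Write p2 and p3 for the event rates in the two phases, the same in every arm (no drug effect). The crude difference is

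(190·p2 + 255·p3)/445 − (95·p2 + 255·p3)/350 = (190/445 − 95/350)(p2 − p3) = 0.156 (p2 − p3).

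**Reading 2: one column per dose.**
- Selected dose versus placebo: 95 + 255 against 95 + 255. The Phase II share is 27.1% in both, so the spurious difference is 0.
- Dropped dose (95, all Phase II) against all-phase placebo: p2 − (95·p2 + 255·p3)/350 = (255/350)(p2 − p3) = 0.729 (p2 − p3).

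**Illustration.** The rates below are assumptions; the documents give none. Each row has no drug effect.

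| Phase II rate | Phase III rate | All SCTA01 | All placebo | Reading 1 difference | Dropped dose minus all placebo |
|---|---|---|---|---|---|
| 25% | 15% | 19.3% | 17.7% | +1.6 points | +7.3 points |
| 30% | 20% | 24.3% | 22.7% | +1.6 points | +7.3 points |
| 50% | 30% | 38.5% | 35.4% | +3.1 points | +14.6 points |
| 30% | 50% | 41.5% | 44.6% | −3.1 points | −14.6 points |

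First row: (190 × 0.25 + 255 × 0.15)/445 = 85.75/445 = 19.3%; (95 × 0.25 + 255 × 0.15)/350 = 62/350 = 17.7%; 25.0% − 17.7% = 7.3 points.

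**With stratification.** The Mantel-Haenszel risk difference weights the within-phase differences by n1·n0/N. For all SCTA01 versus placebo the weights are 190 × 95/285 = 63.3 in Phase II and 255 × 255/510 = 127.5 in Phase III. With no drug effect each within-phase difference is 0, so the combined difference is 0 for every pair of rates.

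**The case against.** The strongest reply is that pooling of doses is not stated. Sections 3.1 and 5.6 treat each dose as its own group, and tabulation by treatment group can mean one column per dose. The main comparison, selected dose versus placebo, is then free of this bias. That stands. It does not settle the dropped dose, whose natural comparator in such a table is a placebo column that is 73% Phase III. The protocol does not prescribe that contrast, but adjacent columns invite it.

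Second, no safety hypothesis test is planned. That also stands: this concerns how descriptive proportions are read, and no error rate is at issue.

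Third, section 8.1 keeps COVID-19 signs, symptoms, sequelae and endpoint-consistent deaths out of the AE data, which removes part of the route by which rates could drift. That limits the likely drift but does not exclude it; a change in premedication practice, for example, would still affect recorded infusion reactions.

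Fourth, table layout usually belongs in a SAP. Sections 9.7.1 and 9.9 do defer detail to one, and section 7.2.3 does so for QTc. Section 9.6 does not, and it describes only general summaries. A SAP could still supply the split, but nothing in the text reviewed commits to it.

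A reader might go further and infer that any between-phase change appears in full as a drug effect. The arithmetic does not support this: the leakage is 16% with merged doses, none for the selected dose in by-dose columns, and 73% only for the dropped dose against all-phase placebo. A reader might also infer that dose selection rests on confounded safety data. It does not: the second interim analysis is done at the end of Phase II, when all groups are concurrent, and the IDMC weighs any safety signal for either dose (section 3.1).

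**Conclusion.** The point holds in limited form. As written, the safety text leaves the columns undefined and makes no allowance for phase. Under either reading at least one crude comparison is not concurrent: all SCTA01 versus placebo if the doses are merged, or the dropped dose versus placebo if they are not.

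Per 10-point change in an event rate between phases, the spurious difference is about 1.6 points in the first case and 7.3 points in the second. Its sign follows the direction of the change, so it can suggest harm or mask it. The allocation shares follow from the protocol's planned numbers. Whether rates change, and by how much, is an assumption. The primary efficacy comparison and the Phase II dose decision are unaffected. I would label this a cheap improvement.

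**What to change.** State in section 9.6, the synopsis and the SAP table shells, before unblinding:
- Safety is tabulated by dose within phase.
- The dropped dose is compared only with concurrent Phase II placebo.
- Where phases are combined, the main display is selected dose versus placebo, which is 1:1 in both phases.
- Any combined comparison, including any table of all SCTA01 versus placebo, reports a phase-stratified (Mantel-Haenszel) risk difference beside the crude percentages.
- If Phase III uses a fixed X mg dose, which sections 3.1 and 5.2 allow, the text says which Phase II column it joins, if any.

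The cost is some wording, a few more tables, and smaller cells in the by-phase displays. No additional patients, data or alpha are needed.

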9.7. Efficacy Analysis

9.7.1. Primary Efficacy Analysis

The primary endpoint is TTCI up to Day 29. TTCI is defined as the time (in days) from randomization to the first day on which a patient satisfies point 1, 2, or 3 on the 8-point ordinal scale and maintains a score ≤ 3 at least 48 hours (initial improvement) and maintains this up to Day 29 (sustained improvement).

All deaths within 29 days or terminated early due to AE will be designated censored at Day 29 with respect to primary endpoint. Any subjects lost to follow-up or terminated early due to other reasons prior to an observed primary endpoint will be censored at the day of their last observed assessment. Subjects who completed follow-up but did not experience a primary endpoint event will be censored at the day of their Day 29 visit. The subjects who take prohibited medications will be regarded as treatment failures and will be censored at the time of medication use.

The primary analysis will use the stratified log rank test to compare treatment group to control group through Day 29 with respect to primary endpoint. Covariate factors may include country, duration of symptoms prior to enrollment, comorbidity and best supportive treatment. Note that if some strata are too small, they might be combined together to allow statistical method work well.

For each group, the Kaplan-Meier estimate of TTCI survival function will be constructed. Hazard ratio of SCTA01 vs. placebo with two-sided 95% CI will be derived from the stratified Cox proportional hazard model. The number of patients with a TTCI event and number of patients censored for the TTCI analysis will be summarized by treatment group.

The sensitivity analyses (such as using different population, different censoring rules and/or different covariates) for the primary endpoint will be fully described in the statistical analysis plan (SAP).

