The primary analysis uses the stratified log rank test to compare treatment group to control group through Day 29 with respect to TTCl. Covariate factors may include country duration of symptoms prior to enrollment, comorbidity and best supportive treatment. Note that if some strata are too small, they might be combined together to allow statistical method work well.

For each group, the Kaplan-Meier estimate of TTCl survival function will be constructed. Hazard ratio of SCTA01 vs. placebo with two-sided 95% CI will be derived from the stratified Cox proportional hazard model. The number of patients with a TTCl event and number of patients censored for the TTCl analysis will be summarized by treatment group. Percentage of subjects in each category using the 8-point ordinal scale up to Day 29 will also be summarized by treatment group.

PK Analysis

Population pharmacokinetic analysis will be performed using NONMEM® (Version 7.4, Icon Inc, PA, USA)..

Immunogenicity Analysis

To collect the proportion of subjects with anti-SCTA01 antibody and to evaluate the change of anti-SCTA01 antibody in patient serum.

Non-Response to SCTA01 assessments

Number and proportion of non-responders having mutations in the gene encoding the SARS-CoV-2 Spike protein through Day 29. A non-responder is defined as a patient who does not achieve a reduction in viral shedding or persistence viral presence or have a rebound in viral shedding following suppression (Phase II, III).

Stopping Infusion Criteria: If a severe allergic reactions (including anaphylaxis) (Grade 3 or higher) is observed during infusion, the infusion will be immediately stopped and no further SCTA01/placebo treatment will be administered to the subject.

TABLE OF CONTENTS

PROTOCOL SYNOPSIS.....	2
TABLE OF CONTENTS	10
LIST OF TABLES	14
LIST OF FIGURES	15
SCHEMA.....	16
ABBREVIATIONS AND DEFINITIONS OF TERMS.....	17
1. STUDY OBJECTIVES AND ENDPOINTS	19
1.1. Primary Objectives	19
1.2. Secondary Objectives	19
1.3. Exploratory Objectives.....	19
1.4. Primary Endpoints.....	19
1.5. Secondary Endpoints.....	19
1.6. Exploratory Endpoints.....	21
2. BACKGROUND	22
2.1. Spike Protein and SARS-CoV-2	22
2.2. Convalescent Plasma in the Treatment of COVID-19	22
2.3. Potential Efficacy	22
2.4. Booster Neutralizing Antibodies against COVID-19.....	23
2.5. SCTA01 is a Neutralizing Antibody against SARS-CoV-2.....	23
2.6. Preclinical Pharmacokinetics	23
2.7. Preclinical Pharmacodynamics	24
2.8. Preclinical Toxicology	26

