3.6.2. Concomitant Therapy

All therapies during the study should be recorded in the source document and eCRF.

Any medication including but not limited to over the counter or prescription medicines, vitamins, and/or herbal supplements, or other specific categories of interest must be recorded along with:

- Drug Name;
- Reason for use;
- Dates of administration including start and end dates;
- Dosage information including administration route, dose and frequency.

Any non-medication interventions must be recorded along with:

- Name of the interventions;
- Reason for use;

- Dates of intervention including start and end dates.

Any experimental treatment, anti-SARS-CoV-2 S protein targeted therapy and use of convalescent plasma are prohibited.

Currently, there are no data on the safety and efficacy of COVID-19 vaccine in persons who have been treated with anti-SARS-CoV-2 antibody. The anti-SARS-CoV-2 antibody like SCTA01 may interfere with the effectiveness of a COVID-19 vaccine. Considering the half-life of SCTA01, COVID-19 vaccination should not be administered for at least 120 days after the administration of SCTA01.

Best Supportive Care for Severe COVID-19:

Best supportive care (BSC) (including medications and non-medication interventions) for severe COVID-19 is allowed based on the local BSC policies or guidelines.

Medications for BSC may be constituted of but not limited to:

- Antiviral Therapy: Remdesivir®; others;
- Immune-Based Therapy: Dexamethasone; Prednisone; Methylprednisolone; Hydrocortisone; others;
- Adjunctive Therapy: Thrombolytic Therapy; others;
- Others.

Non-medication interventions for BSC may be constituted of but not limited to:

- Supplemental oxygen;
- High flow oxygen;
- Non-invasive ventilation;
- Invasive mechanical ventilation;
- ECMO;
- Others.

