4.2. Exclusion Criteria

1. Hospitalized patients who need non-invasive ventilation or high flow oxygen (i.e., 6 point on the 8-point ordinal scale);
2. Patients with critical COVID-19. According to the NIH definition, critical patients are those individuals who have one of the following: 1) respiratory failure and need invasive mechanical ventilation; 2) septic shock; 3) multiple organ dysfunction;
3. Patients with severe COVID-19 who received convalescent plasma or anti-SARS-CoV-2 S protein targeted therapy;
4. ALT or AST is 5 times higher than the upper limit normal range;
5. $\text{eGFR} < 30 \text{ mL/min}$ or on dialysis {eGFR calculated by Cockcroft-Gault formula (*Cockcroft DW, 1976*), Male: $\text{CrCL} (\text{mL/min}) = [(140 - \text{age}) \times \text{weight} (\text{kg})] \times 1/[\text{SCr}]$ }

(mg/dL) \times 72]; Female: CrCL (mL/min) = [(140 - age) \times weight (kg)] \times 0.85 / [SCr (mg/dL) \times 72] };

6. Pregnant or lactating women;
7. Anticipated discharge from the hospital or transfer to another hospital which is not a study site within 72 hours;
8. A patient who is allergic to the active ingredients or components of SCTA01;
9. Patients participated in other clinical studies related to COVID-19 or SARS-CoV-2 infection within 30 days before enrollment or five half-lives of investigational product, whichever is longer.

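### Does the open list of stratification factors for the primary log-rank test call for a change to the plan?

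*Combined protocol and SAP*

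**What the plan says.** Section 9.7.1 compares time to clinical improvement (TTCI) with a stratified log-rank test and takes the hazard ratio from a stratified Cox model. On the factors it says: "Covariate factors may include country, duration of symptoms prior to enrollment, comorbidity and best supportive treatment". The Synopsis repeats this with a comma lost after country ("Covariate factors may include country duration of symptoms prior to enrollment, comorbidity and best supportive treatment"), a typographical slip. Both places add: "Note that if some strata are too small, they might be combined together to allow statistical method work well". Section 9.7.1 then sends the sensitivity analyses to the SAP: "different censoring rules and/or different covariates) for the primary endpoint will be fully described in the statistical analysis plan (SAP".

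Section 5.6 says of each phase: "The randomization schedule will be stratified by country". No other randomization factor is named.

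On best supportive care, the Synopsis (Reference Therapy) says: "Best supportive care is allowed as a base therapy". Section 3.6.2 itemises it under therapy during the study. Medications come first, including antivirals and corticosteroids. The second part opens "Non-medication interventions for BSC may be constituted of but not limited to" and runs to high flow oxygen, non-invasive ventilation, invasive ventilation and ECMO. Section 4.2 excludes "Hospitalized patients who need non-invasive ventilation or high flow oxygen", and Section 7.3.1 makes these supports scores 6 and 7 of the outcome scale. Section 9.7.7 uses best supportive treatment again as a subgroup factor.

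**The concern.** Two things look wrong at first.

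- **Open list.** A confirmatory test should be fixed before anyone sees results by arm. Here the factors are permitted rather than required, the one factor used in randomization is among the optional ones, and pooling has no threshold. Only the sensitivity analyses are expressly deferred to the SAP. If the set were chosen after unblinding, the false-positive rate would exceed the nominal level even with purely baseline factors.
- **Undated factor.** Symptom duration is tied to the time before enrollment, but best supportive treatment is not. If it were coded from the Section 3.6.2 list, the stratum could include escalation to ventilation. That happens after randomization and is part of the outcome scale. Conditioning on it could understate a benefit, or favour a drug that increases escalation.

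**Working it through.** **Step 1: the plan's own figures.** Inputs: 95 + 255 = 350 patients per arm (Section 9.3); RR 1.4, 80% event rate and 31% Phase III information (9.4); boundaries 0.01068 and 0.0166 (9.3); 556 final events (9.7.6).

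- Final events: 0.80 × 700 = 560, against 556 stated.
- Third interim: 0.80 × 190 + 128 = 152 + 128 = 280, as stated.
- Pocock-type spending at t = 0.31: 0.025 × ln(1 + (e − 1) × 0.31) = 0.025 × ln(1.5327) = 0.01068, as stated. The final boundary is 0.0167 at t = 0.31 and 0.0166 at t = 128/408.
- Power at the final boundary: Φ(½√556 × ln 1.4 − 2.130) = Φ(3.967 − 2.130) = Φ(1.837) = 96.7%, consistent with over 90%.

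None of these calculations uses strata, so the open list leaves them untouched.

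**Step 2: choice among baseline factor sets.** Four optional factors give 2⁴ = 16 sets, of which 2³ = 8 contain country. The simulation had no drug effect, 350 per arm, 5 countries with allocation blocked by country, three binary prognostic factors, one look and 6,000 runs. Ranges cover moderate and strong prognostic effects.

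| Strata | Rejects at 0.025 | Rejects at 0.0166 |
|---|---|---|
| None | 1.9–2.4% | 1.1–1.7% |
| Country, fixed | about 2.5% | 1.7% |
| All four, fixed | 2.4–2.7% | 1.6–1.7% |
| Best of 8 with country | 4.5–5.3% | 3.2–3.4% |
| Best of 16 | 4.8–5.6% | 3.5% |

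A second run at 0.0166 used 8 countries and a rate ratio per factor of 1.0/1.5/2.0. Country fixed rejected in 1.8/1.6/1.8%, best of 16 in 3.1/3.9/4.9%, and best of 8 with country in 2.9/3.7/4.4%.

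The fixed sets hold the level. Omitting country does not inflate error, and with strong factors the unstratified test is conservative. All the inflation comes from selecting the largest Z, which requires treatment codes.

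**Step 3: post-randomization coding.** Assumed: stratum = ever escalated; escalated patients improve at 0.3 times the rate of others; 350 per arm; 556 events; cut 0.0166; one look.

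- Escalation 30% placebo, 20% drug, overall RR 1.40: stratified RR 1.29, power 80% against 96% unstratified.
- Escalation 20% placebo, 30% drug, overall RR 1.00: stratified RR 1.14, rejection 28% against 1.8%. A normal approximation with looks at 149, 280 and 556 events lowers the 28% to about 20% if the RR 1.22 futility rule is followed, and to about 18% if the 1.15 rule is followed as well.
- Equal escalation: no power loss, and type I error about 1.7% either way.

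The documents give no coding, escalation rates or factor effects, so these figures show direction only.

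**Step 4: which reading applies.**

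- The other three factors in Section 9.7.1 are baseline characteristics, as are the other subgroup factors in 9.7.7.
- The Synopsis describes supportive care as the base therapy.
- Section 3.6.1 permits and records prior antivirals and corticosteroids, so a baseline version of the variable exists.
- Ventilatory support cannot be a baseline category, because entry requires score 5 (Section 4.1) and 4.2 excludes patients who need more.

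The post-randomization reading is possible in words only.

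**The case for a change.** The strongest case for a change has four parts. The primary strata are nowhere expressly deferred to the SAP. Three unblinded interim analyses are planned, with efficacy review possible at the first. The type I error guarantee in Section 9.7.2.2 presumes that each phase's p-value comes from a test fixed in advance. And closing the list would cost a few sentences. Making country mandatory would not be enough, since the best of the 8 sets with country still rejects in up to 4.4% at 0.0166.

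Of this, the gap in wording stands: nothing in the available text closes the list, gives a pooling rule or dates best supportive treatment. The harm does not follow from it. Section 5.6 keeps allocation confidential until the final analyses from all but the IDMC team and the unblinded statistician, and Section 9.7.5 gives the interim analyses to an external statistician. These safeguards reduce the scope for favourable selection without making it impossible. Planned sensitivity analyses with different covariates also presuppose a defined primary set. The SAP text is not available here, so it cannot be confirmed that it names one.

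A rule of country only, with no other strata, would go beyond filling the gap. Country alone matches the randomization. Adding baseline prognostic factors also holds the error rate in Step 2.

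**Conclusion.** The list is incomplete, but the plan already states the method (stratified log-rank and Cox) and names the candidate factors, with country first. With strata fixed from baseline values before unblinding, the error rate stays at about its nominal level: 2.4–2.7% against 2.5%. The larger figures need steps the plan does not call for. The 3.1–4.9% at 0.0166 assumes the best of 16 sets is always picked with treatment codes in hand. The 28% false rejection and the fall in power from 96% to 80% assume the less natural coding plus a 10-point difference in escalation. This is detail that analysts would be expected to write down while blinded, using the same strata in both phases and in both models. The choice between country alone and country plus baseline factors is a fair trade-off. No change to the plan follows. The conclusion rests on the blinding arrangements being kept and on the baseline reading of best supportive treatment.
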